7.3.3 ON-TREATMENT VISITS

7.3.3.1 Cycle 1; Day 8, 15, 22 and Cycle 2, Day 15)

- Focused physical exam
- Assess and record symptoms
- CBC with differential
- Chemistry profile (sodium, potassium, chloride, creatinine, BUN, total protein, albumin, AST, ALT, alkaline phosphatase, total bilirubin, calcium, CO2)
- LDH, amylase, lipase

7.3.3.2 Cycle 2-3; Day 1

- Record vitals
- Focused physical exam
- Assess and record symptoms
- CBC with differential
- Chemistry profile (sodium, potassium, chloride, creatinine, BUN, total protein, albumin, AST, ALT, alkaline phosphatase, total bilirubin, calcium, CO2)
- LDH, amylase, lipase
- Thiamine level to be checked on Cycle 2, Day 1
- Assess TSS with MPN SAF
- Assess PGIC

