7.3.4 FINAL STUDY VISIT

7.3.4.1 End of Treatment Visit (28 +/- 7 days from study drug completion)

- Record vitals
- Peripheral blood drawn for correlatives
- Physical exam
- Assess and record symptoms
- CBC with differential
- Chemistry profile (sodium, potassium, chloride, creatinine, BUN, total protein, albumin, AST, ALT, alkaline phosphatase, total bilirubin, calcium, CO2)
- LDH

Final instructions will be provided to the patient and the patient will be informed if results will be available or any planned presentation or publication of the study data.

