 - Patients who do not have a TSS score performed at day 84 assessment or who have discontinued study drug prior to day 84 assessment will be considered to not have 50% reduction in TSS.
- Proportion of patients who have a 50% reduction in MPN-SAF TSS from baseline to week 24 in patients with baseline TSS ≥ 10
 - Reduction in MPN-SAF TSS score will be measured by comparing TSS score at day 168 assessment to TSS score on cycle 1 day 1.
 - Only patients with baseline TSS ≥ 10 will be eligible for symptom response.
 - Patients who do not have a TSS score performed at day 168 assessment or who have discontinued study drug prior to day 168 assessment will be considered to not have 50% reduction in TSS.
- Change in TSS from baseline to week 12 in patients with baseline TSS ≥ 10
 - These will be reported as a nominal value calculated by subtracting the TSS on cycle 1 day 1 from the TSS at day 84 assessment. Improvements in TSS will be represented with values less than zero, while progression of symptoms will be represented with values greater than zero.
 - All enrolled patients' baseline TSS ≥ 10 and documented day 84 TSS will be included in this analysis.
 - Patients who do not have a TSS score performed at day 84 assessment or who have discontinued study drug prior to day 84 assessment will not be included in this analysis.
- Change in TSS from baseline to week 24 in patients with baseline TSS ≥ 10
 - These will be reported as a nominal value calculated by subtracting the TSS on cycle 1 day 1 from the TSS at day 168 assessment. Improvements in TSS will be represented with values less than zero, while progression of symptoms will be represented with values greater than zero.
 - All enrolled patients' baseline TSS ≥ 10 and documented day 168 TSS will be included in this analysis.
 - Patients who do not have a TSS score performed at day 168 assessment or who have discontinued study drug prior to day 168 assessment will not be

- included in this analysis.
- Change in TSS from baseline to time of best response in patients with baseline TSS ≥ 10
 - These will be reported as a percent change from the baseline value by subtracting the TSS on cycle 1 day 1 from the lowest TSS score documented for the patient between cycle 2 day 1 and cycle 7 day 1 and dividing the difference by the baseline TSS score. Improvements in TSS will be represented with values less than zero, while progression of symptoms will be represented with values greater than zero.

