 - All enrolled patients' baseline TSS ≥ 10 and at least one other documented TSS score after cycle 1 will be included in this analysis.
 - Patients who do not have a TSS score documented at or beyond cycle 2 day 1 will not be included in this analysis.
- Patient's global impression of change (PGIC) at week 12
 - This will be measured using the validated questionnaire wherein patients are asked about the change in their myelofibrosis symptoms since starting on the study. Patients can choose from one of seven potential answers: Very much improved, Much improved, Minimally improved, No change, Minimally worse, Much worse, Very much worse.
 - This will be reportedly qualitatively wherein the number of patients choosing particular answers will be tabulated and frequencies will be reported.
- PGIC at week 24
 - This will be measured using the validated questionnaire wherein patients are asked about the change in their myelofibrosis symptoms since starting on the study. Patients can choose from one of seven potential answers: Very much improved, Much improved, Minimally improved, No change, Minimally worse, Much worse, Very much worse.
 - This will be reportedly qualitatively wherein the number of patients choosing particular answers will be tabulated and frequencies will be reported.

The analysis of binary endpoint including spleen response will be analyzed by the exact binomial distribution. The change of baseline to week 12 or 24 of the continuous variables including patient-reported outcomes (PROs) will be examined by paired-t test or Wilcoxon signed-rank test, as appropriate.

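### Change in TSS at weeks 12 and 24 is a paired test in patients still on drug; it leaves early stoppers' on-treatment scores unused and is likely, though not certain, to overstate improvement

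*Combined protocol and SAP*

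**What the plan says.** Section 10.4.3 defines three TSS-change endpoints, all in patients with baseline TSS of at least 10.

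- **Week 24, inclusion.** Patients with that baseline "and documented day 168 TSS will be included in this analysis". Nothing is said about being on drug.
- **Week 24, exclusion.** Patients with no day-168 score, or who "have discontinued study drug prior to day 168 assessment will not be" included. The two conditions are joined by an or, so read literally a recorded score does not rescue a patient who has stopped.
- **Week 12.** The same pair of bullets; the exclusion begins "Patients who do not have a TSS score performed at day 84 assessment or who" and goes on to patients who stopped drug before day 84.
- **Best response.** Patients with baseline TSS of at least 10 and "at least one other documented TSS score after cycle 1 will be included in this analysis". Stopping drug does not exclude anyone here.

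The week-12 and week-24 changes "will be examined by paired-t test or Wilcoxon signed-rank test, as appropriate". No model across visits and no sensitivity analysis is planned.

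The instruction "Assess TSS with MPN SAF" appears in section 7.3.3.2 (cycles 2 and 3, day 1) and again for cycles 4 to 7, and later visits are every three cycles. All of this is on treatment. The end-of-treatment visit (7.3.4.1) lists items such as "Peripheral blood drawn for correlatives" but no MPN-SAF, and section 7.3.5 leaves assessments after early termination to the physician.

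**The concern.** Patient-reported outcome is a named secondary objective, and the trial has no control arm to offset selective loss. The protocol itself ties stopping to symptoms. Under section 5.4.1, progression and unacceptable adverse events require discontinuation. In Appendix H a TSS rise of at least 50% is a minor progression criterion. Section 2.3.1 says gastrointestinal events are most frequent in the first two cycles and that grade 3 to 4 events have led to discontinuation; the TSS in Appendix C includes early satiety, abdominal discomfort and weight loss. Patients who feel worse are therefore more likely to be missing from the week-12 and week-24 means, and the paired p-value then describes a selected group.

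**Working it through.** **Plan's own figure.** There is none for TSS. The only design calculation is for the primary response rate. It reproduces: summing P(X1 = x)·P(X2 ≥ 12 − x) over x = 3 to 9, with 9 then 16 patients, gives type I error 0.0421 at 30% and power 0.8007 at 55%. It has no bearing on this point.

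**Step 1. The two bullets side by side** (baseline TSS of at least 10).

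| Patient at the visit | Inclusion bullet | Exclusion bullet |
|---|---|---|
| On drug, scored | in | in |
| On drug, not scored | out | out |
| Off drug, not scored | out | out |
| Off drug, scored | in | out |

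Only the last row conflicts. Since no TSS is scheduled after stopping, it will hold few patients.

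**Step 2. What goes unused.** A patient who stops late in cycle 3 has scores from day 1 of cycles 2 and 3 and enters neither endpoint. A patient who stops late in cycle 5 has four post-baseline scores (day 1 of cycles 2 to 5); the week-12 score enters the week-12 test, but none informs week 24.

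**Step 3. Size by identity.** Let d be the fraction stopped, m_c the completers' mean change and m_s the stoppers' mean change. Then

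mean over all = (1 − d)·m_c + d·m_s, so overstatement = d·(m_s − m_c).

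The documents give none of these inputs. Section 10.5 expects dropout below 10%, but for accrual planning; it is not a week-24 discontinuation rate. Assume m_c = −8 on the 0 to 100 scale (ten items scored 0 to 10).

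| d | m_s = −8 | m_s = −4 | m_s = 0 | m_s = +4 |
|---|---|---|---|---|
| 10% | 0 | 0.4 | 0.8 | 1.2 |
| 20% | 0 | 0.8 | 1.6 | 2.4 |
| 30% | 0 | 1.2 | 2.4 | 3.6 |
| 40% | 0 | 1.6 | 3.2 | 4.8 |

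**Step 4. Size by simulation.** Assumptions: 4,000 trials per scenario, 25 patients (an upper bound, since entry on spleen criteria alone is allowed), six visits, SD of change 10, first-order autoregressive correlation 0.6, and stopping that depends on the last observed change.

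| True change | Stopped | Completers | All patients | Overstatement |
|---|---|---|---|---|
| 0 | 10.6% | −0.164 | 0.037 | 0.201 |
| 0 | 11.8% | −0.373 | 0.014 | 0.387 |
| 0 | 31.8% | −0.667 | 0.002 | 0.669 |
| 0 | 34.0% | −1.078 | −0.007 | 1.071 |
| −8 | 8.4% | −8.130 | −7.968 | 0.162 |
| −8 | 7.8% | −8.221 | −8.004 | 0.217 |
| −8 | 25.8% | −8.390 | −7.930 | 0.460 |
| −8 | 24.4% | −8.667 | −7.969 | 0.698 |

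These are smaller than Step 3 because the implied gap between stoppers and completers is only about 2 to 3 points (for example 0.669/0.318 = 2.1 and 1.071/0.340 = 3.2). With no true change and 34% stopped, the paired t test declared improvement in 6.5% of trials against a nominal 2.5%. With stopping unrelated to symptoms the bias was about zero. A likelihood-type estimate using every visit up to stopping stayed within about 0.04 points of the all-patient mean, in a setting where stopping depended only on observed scores.

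**The case against.** The strongest case against is that these are secondary, unpowered endpoints on which no decision rests, and that stopping is already treated strictly elsewhere: the 50%-reduction endpoints count stoppers as failures, and discontinuation reasons are reported (section 10.4.5). A responder proportion with failures imputed and an on-treatment mean can stand together as complementary summaries. That stands, and it limits the importance of the point.

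Several stronger readings are tempting but not supported:

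- That every TSS-change endpoint drops stoppers. The best-response endpoint keeps them, and it also uses the cycle 2 to 7 scores.
- That many recorded scores are thrown away after stopping. None is scheduled, and the week-24 assessment has a window of 14 days either side, so a patient scored at that visit before stopping is not excluded.
- That TSS is available every cycle throughout. This holds only to cycle 7 and only on treatment.
- That lack of response removes patients before the week-24 score. That rule in section 5.4.1 applies at the week-24 assessment itself.
- That overstatement is demonstrated. A TSS rise is one minor progression criterion among several, and some stopping may have nothing to do with symptoms.

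A repeated-measures model also has limits with at most 25 patients. An unstructured covariance over six visits has 6 × 7/2 = 21 parameters, and the model assumes data missing at random. Both limits are real and shape the fix.

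**Conclusion.** The point holds for two of the three TSS-change endpoints. As written, the week-12 and week-24 changes are estimated only in patients still on drug and scored, the two governing bullets conflict for one small group, and on-treatment scores already collected from early stoppers are not used at the visit they miss. The likely direction is towards benefit, because the protocol links stopping to worsening symptoms and to toxicity; the documents do not prove it.

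No size can be computed from the documents. Combining the simulation and the arithmetic, the overstatement is roughly 0.2 to 1.2 points at about 10% stopping and about 0.5 to 3.6 points at 20 to 30%. At 40% it would be 3.2 points for an 8-point gap and 4.8 for a 12-point gap. It is zero if stoppers changed as much as completers. The upper figures need a large assumed gap and are not estimates for this trial. This is a worthwhile, inexpensive improvement to a secondary analysis; it does not touch the primary endpoint.

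**What to change.** In section 10.4.3:

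1. Delete the exclusion of patients off drug who have a documented score at the visit, so that the two bullets agree.
2. Estimate week-12 and week-24 change from one repeated-measures model on the scheduled visits (day 1 of cycles 2 to 7), in all patients with baseline TSS of at least 10 and any post-baseline score. Use baseline TSS as covariate and visit as factor, with a prespecified simple covariance structure (for example first-order autoregressive) and a small-sample degrees-of-freedom correction. State what the estimate is meant to describe once drug is stopped.
3. Keep the paired t or signed-rank test as a sensitivity analysis.
4. Add a missing-not-at-random sensitivity analysis, for example by shifting stoppers' unobserved changes towards worsening by fixed amounts such as the 4, 8 and 12 points used above.
5. Report the number without a score at each visit, with reasons.

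The cost is SAP wording and modest extra analysis, with no new data. The reported mean improvement may be smaller, and the main model rests on missing at random. Adding the questionnaire to the end-of-treatment visit is optional: that visit falls 28 ± 7 days after the last dose and would measure an off-drug state.

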10.4.4 SAFETY ANALYSES

Using summary statistics, safety data will be coded using CTCAE 5.0 criteria, with each AE being counted only once for a given participant. The severity, frequency, duration, outcome and relationship of AEs to the study agent, as defined by the treating investigator, will be presented by System Organ Class (SOC) and preferred term groupings. Adverse events leading to premature discontinuation from the study drug, adverse events of special interest, and serious treatment-emergent AEs will be presented in a table.

The proportion of patients experiencing grade ≥ 3 AEs will be calculated and presented separately in a table. Hematologic grade ≥ 3 AEs will be included if not present at baseline.

Hematologic values (hemoglobin, WBC, platelet count) will be calculated at the beginning of each cycle with median values being presented as a function of time while receiving treatment with study drug.

10.4.5 ADHERENCE AND RETENTION ANALYSES

The investigator or his/her designated and qualified representatives will administer/dispense study drug only to patients enrolled in the study in accordance with the protocol. The study drug must not be used for reasons other than that described in the protocol. To document compliance with the treatment regimen, patients will be instructed to return all fedratinib bottles (empty, partially filled or full), to the study site personnel prior to each visit and at the treatment completion visit. The site staff will document the bottles returned and the number of capsules per bottle on the appropriate form. Compliance below 80% require counseling of the patient by study site personnel.

Reason for treatment discontinuation will be documented in the treatment completion visit. This will be reported descriptively.

10.4.6 BASELINE DESCRIPTIVE STATISTICS

Planned baseline demographic and clinical information will include age, gender, specific disease-associated mutations, cytogenetics, prior therapies, spleen size, hematologic laboratory parameters (hemoglobin, WBC, immature myeloid cell percentage, platelet, peripheral blast percentage), LDH, bone marrow/aspirate parameters (blast percentage, fibrosis grade, ring sideroblast percentage, cellularity).

Demographics will be presented using summary statistics.

10.4.7 PLANNED INTERIM ANALYSES

The interim efficacy review will take place after 9 patients are evaluable for efficacy (i.e., completed week 24 disease assessment or discontinued study treatment prior to week 24). Enrollment will be halted if there are ≤ 2 responses among the first 9 patients. Enrollment will not be stopped while waiting for the first 9 patients to become evaluable for efficacy. If ≥ 3 responses are seen in the first 9 patients, an additional 16 patients will be enrolled for a total enrollment of 25 patients.

Overall response data will be presented in aggregate.

Individual patient TSS, PGIC will be measured at week 12 and week 24 assessment and presented as a function of time.

10.4.11 EXPLORATORY ANALYSES

- Overall Survival: OS will be measured for each patient on the study. OS will be defined as time from first treatment to death due to any cause or censored at last follow-up. OS will be measured by Kaplan-Meier method. Median OS, as well as OS rate at 1-year and 2-year will be reported

descriptively. The confidence interval will be computed by log-log transformation.

- Progression free survival: Progression will be measured for each patient as defined by Modified MDS/MPN IWG Proposed Criteria for Disease Progression in adult MDS/MPNs (Appendix H). PFS will be defined as time from first treatment to progression or censored at last follow-up. PFS will be measured by Kaplan-Meier method. Median PFS, as well as PFS at 1-year and 2-year will be reported descriptively. The confidence interval will be computed by log-log transformation.
- Duration of response: Response duration will be measured for each responding patient. Response and progression will be defined by Modified MDS/MPN IWG Proposed Criteria.¹ Duration of response is defined as the amount of time from the date of initial response to the date of disease progression or death.
- Correlation between mutations detected from NGS at baseline and response will be assessed using contingency tables and Mantel-Haenszel test to calculate relative risk and p-values.
- Correlation between the number of mutations detected from NGS at baseline and response will be assessed using cut-points of 2 and 3 mutations with relative risk and p-values calculated using contingency tables and Mantel-Haenszel test.
- For correlative study, the primary endpoint is the response. The difference between vehicle and fedratinib will be examined by Mantel-Haenszel test. The difference in survival between arms will be evaluated by the log-rank test. In addition, the agreement between PDX mouse response and patients' response will be measured by Kappa index.

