7.1.14 Correlative Studies

Next-generation sequencing (NGS) will be performed on a bone marrow aspirate or peripheral blood sample during screening and after cycle 6. NGS will be performed per institutional standards. Acceptable NGS platforms must include testing for the following genes with sensitivity of at least 5%: JAK2, MPL, CALR, TET2, DNMT3A, ASXL1, EZH2, SRSF2, U2AF1, ZRSR2, SF3B1, RUNX1, CSF3R, KRAS, NRAS, CBL, PTPN11, TP53, PHF6, IDH1, IDH2, ETV6, SETBP1. If NGS has been performed within 12 months of screening, this may be used as baseline NGS if approved by PI.

Mononuclear cells from bone marrow aspirate will be collected at screening and used to develop PDX mouse models for each enrolled patient. Samples will be under the care of [name] lab.

To determine whether PDX models recapitulate responses to study drug in patients with MDS/MPN and CNL, we will obtain purified hCD34+ cells from each primary pre-treatment patient sample. These cells will be sent to the lab of [name] at Moffitt Cancer Center where they will be xenografted into 6 NSGS vehicle- and 6 fedratinib-treated mice. After 7 days of transplantation and peripheral blood analysis to assess for hCD45 cell engraftment, we will treat NSGS mice with fedratinib at pharmacologically comparable doses to that exposed to the patient on clinical study. Treatment would occur until the animal becomes moribund. PDX response assessment would be measured in three categories compared to vehicle: 1.) Reduction in splenomegaly as measured by spleen weight at necropsy and MRI at baseline and at the time that the first mouse becomes moribund. MRI experiments will be done on a 7T horizontal magnet (Agilent Technologies) using a 35 mm 1H birdcage coil (Doty Scientific). 2) Improvement in hematologic parameters (to include anemia, thrombocytopenia, WBC count, monocyte count). 3) Improvement in BM pathology to include decreases in bone marrow myeloblasts (hCD34+) and resolution of dysplasia/fibrosis. We will also measure survival of each treatment cohort of mice. These responses will then be compared to those seen in the clinical trial to determine the ability for the NSGS PDX to recapitulate drug response.

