Patients enrolled after the interim analysis of nine patients will have purified hCD34+ cells from primary pre-treatment samples xenografted into an additional 6 NSGS mice that will be treated with ruxolitinib. These mice will be subjected to the same procedures as the vehicle- and fedratinib-treated mice in an effort to directly compare the efficacy of ruxolitinib and fedratinib in PDX mouse models of MDS/MPN and CNL.

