10.4 DESCRIPTION OF STATISTICAL METHODS

10.4.1 GENERAL APPROACH

This will be a phase 2 trial to assess the efficacy of fedratinib in MDS/MPN and CNL. Patients with a

diagnosis of MDS/MPN-U, aCML, MDS-MPN-RS-T, or CNL will be enrolled using modified Simon's minimax 2-stage approach.³¹ The primary endpoint of the study is the proportion of patients achieving an objective clinical response at week 24 which is determined based upon the Modified MDS/MPN IWG Proposed Response Criteria.

An interim analysis will be performed after 9 patients have completed their week 24 disease assessment or have discontinued study treatment prior to week 24 to assess for futility. If there are ≥ 3 responses among these 9 patients, an additional 16 patients will be enrolled for a total of 25. This will be sufficient to test our hypothesis that fedratinib will increase the ORR from a historical standard of 30% to 55% using a power of 80% and a one-sided type 1 error rate of 0.05. The null hypothesis will be rejected if 12 or more responses are observed.

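### The exploratory PDX mouse survival comparison names a log-rank test with no donor stratum, although every donor supplies six mice to each arm

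*Combined protocol and SAP*

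**What the plan says.** **The experiment (section 7.1.14).** Purified cells from each patient are "xenografted into 6 NSGS vehicle- and 6 fedratinib-treated mice". Patients enrolled after the interim analysis of nine also have cells "xenografted into an additional 6 NSGS mice that will be treated with ruxolitinib", with the stated purpose of comparing the two drugs directly. Mice are treated until moribund. Of survival the section says: "We will also measure survival of each treatment cohort of mice".

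**The analysis (section 10.4.11).** For survival: "The difference in survival between arms will be evaluated by the log-rank test". For response: "The difference between vehicle and fedratinib will be examined by Mantel-Haenszel test". For agreement with the patients, PDX mouse response and patient "response will be measured by Kappa index". No sentence names donor as a stratum, a frailty term or a cluster adjustment, or states the unit of analysis.

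**The number of donors (sections 10.4.1 and 10.4.7).** If at least 3 of the first 9 patients respond, "an additional 16 patients will be enrolled for a total of 25". Enrolment stays open while those 9 mature.

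**The concern.** The experiment is matched by donor: within each donor the arms differ only in treatment. Mice from one donor share one disease, and section 2 describes these diseases as heterogeneous and molecularly complex, so donor-to-donor differences in mouse survival are to be expected.

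A log-rank test that pools all mice treats donor variation as noise. The arms are balanced within donor, so pooling does not create false positives when the drug effect is common to all donors; it makes the test conservative and weak. At stake is a missed vehicle-versus-fedratinib effect in the very comparison that the matching was meant to sharpen.

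The ruxolitinib arm raises a different problem. It exists only for later donors. A pooled comparison would set fedratinib mice from all donors against ruxolitinib mice from a subset, so a difference between donors could appear as a difference between drugs.

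**Working it through.** **Inputs from the documents.** 6 mice per arm per donor (7.1.14); 9 donors if the trial stops at the interim, 25 if it runs in full (10.4.1). The plan gives no power, hazard ratio, alpha or intra-donor correlation for the PDX work, so there is no PDX figure to reproduce.

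**Assumptions.** Hazard ratio 0.70, common to all donors; two-sided alpha 0.05; exponential survival; no censoring; every graft takes. The donor effect on the log hazard is normal with variance ICC/(1−ICC) × π²/6.

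**Step 1: donors do not differ (closed form).**
- Pooled test: 25 × 12 = 300 deaths. Information is 300/4 = 75. Then |ln 0.70| × √75 = 0.357 × 8.66 = 3.09, and power = Φ(3.09 − 1.96) = Φ(1.13) = 87%.
- Stratified test: with 12 mice split 6/6, the expected null information per donor is (3/11) × Σ(1 − 1/n) for n = 1 to 12, which is (3/11) × (12 − 3.103) = 2.43, against 12/4 = 3 when pooled (81%). Then 0.357 × √(25 × 2.43) = 2.78, and power = Φ(0.82) = 79%.

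So stratifying costs 7 to 8 points when there is no donor effect.

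**Step 2: donors differ (simulation).** The donor's own hazard cancels within a stratum, so stratified power barely moves. Pooled power falls.

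| Assumed ICC | Pooled power | Stratified power |
|---|---|---|
| 0 | 87% | 80% |
| 0.05 | 82% | 79% |
| 0.2 | 70% | 78% |
| 0.5 | 38% | 79% |

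At ICC 0.5 the pooled test's actual size is about 0.6% instead of 5%; the stratified test stays at about 5%. With 9 donors and ICC 0.5, pooled power is about 13–15% against 38–41% stratified.

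**Step 3: a different donor model.** With gamma frailty, 25 donors and a hazard ratio of 0.724 (set for 80% power with independent mice), pooled power is 0.79, 0.63, 0.49, 0.26 and 0.06 at Kendall's tau 0, 0.11, 0.20, 0.33 and 0.50, against about 0.71 stratified throughout. The pattern does not depend on the normal donor effect.

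**Step 4: fedratinib versus ruxolitinib, no true difference.** There are 25 fedratinib donors. At most 25 − 9 = 16 have a ruxolitinib arm, and fewer if patients enter while the first 9 mature; 8 is used here as an assumed low case.

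| Donors with ruxolitinib | Pooled false-positive rate, ICC 0.05 to 0.5 | Shared donors only, stratified |
|---|---|---|
| 16 | about 5–8% | about 5% |
| 8 (assumed) | about 7–20% | about 5% |

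**Step 5: drug effect varies by donor, mean effect zero.** With an SD of the log hazard ratio of 0.3 to 0.8, the stratified test rejects in about 7–17% of runs and the pooled test in about 3–26%. Neither generalises to new donors without a donor-level or cluster-robust analysis.

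**The case against.** **The plan does not say that donors are ignored.** This stands in part. That the test is unstratified is inferred from silence, and 7.1.14 does not settle whether survival is compared per donor or pooled. But the per-donor reading gives up to 25 tests of 6 against 6 with no rule for combining them. Either reading needs a sentence, and a stratified test meets the need.

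**The replacement is not free of problems.** This stands. It loses power when donors hardly differ, and it over-rejects when the drug effect varies by donor. The pooled test is not protected in that case either, so the answer is a sensitivity analysis.

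**No fedratinib-ruxolitinib test is specified.** True: 10.4.11 names only vehicle versus fedratinib for response. But 7.1.14 announces the direct comparison, and the survival sentence speaks of arms without limiting them. With 16 donors the distortion is small.

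**A reader might go further on kappa.** If kappa were computed on mouse-level pairs and tested, each patient's single response would count six times. At an assumed ICC of 0.5 the design effect is 1 + 5 × 0.5 = 3.5, and a nominal 5% test would reject about 30% of the time. The documents do not support that reading. Section 10.4.11 plans no test of kappa and states no mouse-level unit. Section 4.2.3 describes individually matched models, and 7.1.14 defines PDX response relative to vehicle; both point to one PDX result per patient. At that level the false-positive rate of such a test would be about 4–5.5% whatever the ICC.

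**A reader might also take the Mantel-Haenszel test as unstratified**, since the section uses the same name for the mutation tables. Its strata are simply unnamed, and the method is built for stratified tables.

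**Conclusion.** The point holds for the log-rank test. As written and run on pooled mice, it discards the donor matching. The result ranges from a gain of about 7 to 8 points of power when donors do not differ, through a loss of about 8 points at ICC 0.2, to a loss of about 41 points at ICC 0.5 (25 donors, hazard ratio 0.70). These are values at assumed correlations and not limits; the documents support no single figure, such as a halving of power, as the effect. For vehicle versus fedratinib the error is towards missing an effect, provided the drug effect is common to all donors. The ruxolitinib confounding is real but small if 16 donors have that arm, and material only if far fewer do.

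The kappa and Mantel-Haenszel sentences need clarification only. Severity is minor: the work is exploratory, section 3 makes the PDX correlation subject to feasibility, and neither the primary endpoint nor the interim rule is touched.

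**What to change.** Replace the survival sentence in 10.4.11 with:

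> Mouse survival will be compared by a log-rank test stratified by patient donor. Fedratinib and ruxolitinib will be compared only within donors that have both arms, stratified by donor. A donor-level or cluster-robust analysis will be reported as a sensitivity analysis.

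As clarifications, state that the Mantel-Haenszel test for mouse response is stratified by donor, and that kappa uses one PDX result per patient, with the rule that turns the six fedratinib mice into that result.

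The cost is wording only; no mice, samples or patients are added. The price is the power lost if donors prove alike, and the ruxolitinib comparison will leave out fedratinib mice from donors without a ruxolitinib arm.
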